#### **9.4.2. Safety Analysis**

Frequency of grade 3 or higher adverse events will be tabulated as will all grade 1 and 2 adverse events with frequency greater than 5%, e.g. occurring in 2 or more individuals.

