## Cytopenias

Treatment-emergent Grade 3 or 4 cytopenias (neutropenia, thrombocytopenia, and anemia) were reported in subjects treated with ibrutinib. Monitor complete blood counts monthly.

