#### *PROTOCOL SPECIFIC*

##### *Laboratory*

1. Adequate hematologic function independent of transfusion and growth factor support for at least 7 days prior to screening and randomization, with the exception of PEGylated G-CSF (pegfilgrastim) and darbopoietin which require at least 14 days prior to screening and randomization defined as:
  - Absolute neutrophil count  $>750 \text{ cells/mm}^3$  ( $0.75 \times 10^9/\text{L}$ ).
  - Platelet count  $>50,000 \text{ cells/mm}^3$  ( $50 \times 10^9/\text{L}$ ).
  - Hemoglobin  $>8.0 \text{ g/dL}$ .
2. Adequate hepatic and renal function defined as:

- Serum aspartate transaminase (AST) or alanine transaminase (ALT)  $\leq 3.0 \times$  upper limit of normal (ULN).
- Estimated Creatinine Clearance  $\geq 30$  ml/min (Cockcroft-Gault)
- Bilirubin  $\leq 1.5 \times$  ULN (unless bilirubin rise is due to Gilbert's syndrome or of non-hepatic origin)

3. PT/INR  $< 1.5 \times$  ULN and PTT (aPTT)  $< 1.5 \times$  ULN.

*Demographic*

4. Men and women  $\geq 18$  years of age.
5. Eastern Cooperative Oncology Group (ECOG) performance status of 0, 1 or 2.

*Ethical/Other*

6. Female subjects who are of non-reproductive potential (i.e., post-menopausal by history - no menses for  $\geq 1$  year; OR history of hysterectomy; OR history of bilateral tubal ligation; OR history of bilateral oophorectomy). Female subjects of childbearing potential must have a negative serum pregnancy test upon study entry.
7. Male and female subjects who agree to use highly effective methods of birth control (e.g., condoms, implants, injectables, combined oral contraceptives, some intrauterine devices [IUDs], sexual abstinence, or sterilized partner) during the period of therapy and for 90 days after the last dose of study drug
8. Sign (or their legally-acceptable representatives must sign) an informed consent document indicating that they understand the purpose of and procedures required for the study and are willing to participate in the study.

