### 5.3.1.5. Dose Modification for Adverse Reactions

The dose of study drug should be modified according to the dose modification guidelines in Table 1 if any of the following toxicities occur:

- Grade 4 ANC (<500/ $\mu$ L) for more than 7 days. See Section 6 for instructions regarding the use of growth factor support.
- Grade 3 thrombocytopenia (<50,000/ $\mu$ L) in the presence of clinically significant bleeding events.
- Grade 4 thrombocytopenia (<25,000/ $\mu$ L).
- Grade 3 or 4 nausea, vomiting, or diarrhea if persistent, despite optimal anti-emetic and/or anti-diarrheal therapy.
- Any other Grade 4 or unmanageable Grade 3 toxicity.

For Grade 3 or 4 atrial fibrillation or persistent atrial fibrillation of any grade, consider the risks and benefits of ibrutinib treatment. If clinically indicated, the use of anticoagulants or antiplatelet agents may be considered for the thromboprophylaxis of atrial fibrillation (Section 6.2.4).

Table 1. Ibrutinib Dose Modifications

Occurrence	Action to be Taken
First	Withhold study drug until recovery to Grade $\leq$ 1 or baseline; may restart at original dose level
Second	Withhold study drug until recovery to Grade $\leq$ 1 or baseline; may restart at 1 dose level lower (i.e. 420 mg/day for 560 mg /day dose )
Third	Withhold study drug until recovery to Grade $\leq$ 1 or baseline; may restart at 1 dose level lower (i.e. 280 mg/day for 420 mg /day dose )
Fourth	Discontinue study drug

*A high number of circulating malignant cells (>400,000/ $\mu$ L) may confer increased risk of leukostasis; these subjects should be closely monitored. Administer supportive care such as hydration and/or leukaphoresis as indicated. Ibrutinib may be temporarily held, and principal investigator should be contacted.*

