### **9.2. Design**

This is a multicenter, single arm, single stage phase II study designed to estimate the efficacy of ibrutinib in evaluable patients with relapsed, refractory Hodgkin's lymphoma. A participant will be deemed response evaluable if he/she has completed at least one cycle of therapy, has at least one imaging study (CT, MRI or PET) and has not missed >25% of treatment dose (14 doses) prior to cycle 3 day 1. Any participant receiving at least 1 dose of ibrutinib will be considered evaluable for toxicity analysis.

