### 10.1.1 Adverse Events

An AE is any untoward medical occurrence in a subject administered a pharmaceutical product and which does not necessarily have a causal relationship with this treatment. An AE can therefore be any unfavorable and unintended sign (including a clinically significant abnormal laboratory finding, for example), symptom, or disease temporally associated with the use of an investigational study drug, whether or not considered related to the study drug ([ICH-E2A, 1995](#)).

For the purposes of this clinical study, AEs include events which are either new or represent detectable exacerbations of pre-existing conditions.

The term “disease progression” should not be reported as an adverse event term. As an example, “worsening of underlying disease” or the clinical diagnosis that is associated with disease progression should be reported.

Adverse events may include, but are not limited to:

- Subjective or objective symptoms provided by the subject and/or observed by the Investigator or study staff including laboratory abnormalities of clinical significance.
- Any AEs experienced by the subject through the completion of final study procedures.
- AEs not previously observed in the subject that emerge during the protocol-specified AE reporting period, including signs or symptoms associated with the underlying disease that were not present before the AE reporting period
- Complications that occur as a result of protocol-mandated interventions (e.g. invasive procedures such as biopsies).

The following are NOT considered AEs:

- **Pre-existing condition:** A pre-existing condition (documented on the medical history CRF) is not considered an AE unless the severity, frequency, or character of the event worsens during the study period.

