### 10.1.3 Severity Criteria (Grade 1-5)

Definitions found in the Common Terminology Criteria for Adverse Events version 4.03 (CTCAE v m 4.03) will be used for grading the severity (intensity) of *nonhematologic* AEs. The CTCAE v 4.03 displays Grades 1 through 5 with unique clinical descriptions of severity for each referenced AE. Should a subject experience any AE not listed in the CTCAE v m4.03, the following grading system should be used to assess severity:

- Grade 1 (Mild AE) – experiences which are usually transient, requiring no special treatment, and not interfering with the subject's daily activities

- Grade 2 (Moderate AE) – experiences which introduce some level of inconvenience or concern to the subject, and which may interfere with daily activities, but are usually ameliorated by simple therapeutic measures
- Grade 3 (Severe AE) – experiences which are unacceptable or intolerable, significantly interrupt the subject's usual daily activity, and require systemic drug therapy or other treatment
- Grade 4 (Life-threatening or disabling AE) – experiences which cause the subject to be in imminent danger of death
- Grade 5 (Death related to AE) – experiences which result in subject death

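### The safety analysis uses only reported adverse events and leaves the scheduled blood counts unanalysed, so asymptomatic grade 3-4 cytopenia could be under-reported

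*Combined protocol and SAP*

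**What the plan says.** **Risk and objective.** Section 1.5.1 states: "Treatment-emergent Grade 3 or 4 cytopenias (neutropenia, thrombocytopenia, and anemia) were reported in subjects treated with ibrutinib". Section 2.2 makes the safety and tolerability of 560 mg a secondary objective.

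**Collection.** Appendix 1 schedules hematology (white count with differential, hemoglobin, hematocrit, platelets) at screening, days 1 and 15 of cycles 1 and 2, day 1 of cycles 3 to 14, odd-numbered cycles from 15, and some later visits.

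**Analysis.** Section 9.4.2 reads: "Frequency of grade 3 or higher adverse events will be tabulated as will all grade 1 and 2 adverse events with frequency greater than 5" per cent. It equates that threshold with at least 2 patients. The population is set in Section 9.2: "Any participant receiving at least 1 dose of ibrutinib will be considered evaluable for toxicity analysis". Neither Section 9 nor the synopsis plans a laboratory summary, a laboratory-derived grade or a shift from baseline.

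**What counts as an AE.** Section 10.1.1 includes "any unfavorable and unintended sign (including a clinically significant abnormal laboratory finding, for example". Its list of examples and Section 10.3.1 attach the same qualifier to laboratory results. None of them defines it.

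**Grading.** Section 10.1.3 says that CTCAE 4.03 "will be used for grading the severity (intensity) of *nonhematologic* AEs". Section 7.1.1 (Treatment Phase) applies CTCAE 4.03 to AE information with no hematologic exception. Section 5.3.1.5 gives numeric grades for neutrophils and platelets.

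**Entry.** Section 4.1 admits patients with a neutrophil count just above 750 and platelets just above 50,000 per cubic millimetre.

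**The concern.** A measured low count enters the safety table only after an investigator has judged it to be an AE and graded it. The first step rests on an undefined term. An asymptomatic grade 3-4 value could be recorded at one of the four institutions and not at another. In that case the tabulated cytopenia rate would partly reflect recording practice. With a single arm, there is no comparator in which such differences could cancel.

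There is a second limit even if every abnormal count is recorded. The patients are heavily pretreated, some have had a transplant, and they may enter with low counts. A frequency of AEs says who crossed a grade, but not from what starting value.

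The grading text is a separate inconsistency. A table built on grade 3 or higher needs one rule for what grade 3 is.

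**Working it through.** **1. The plan's own figure.** The only number in Section 9.4.2 is the grade 1-2 threshold: above 5%, given as 2 or more individuals. With 35 patients, 5% × 35 = 1.75. One patient is 1/35 = 2.9% and two are 2/35 = 5.7%, so the threshold is right. It also holds at 31 patients (1/31 = 3.2%, 2/31 = 6.5%). No stated figure is wrong. The point is what goes into the table.

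**2. From measured count to table.**

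| Step | Source | Depends on |
|---|---|---|
| Count measured | Appendix 1 | Schedule |
| Count recorded as an AE | 10.1.1, 10.3.1 | Clinical significance, undefined |
| AE graded | 10.1.3, 7.1.1, 5.3.1.5 | Sections that disagree |
| AE tabulated | 9.4.2 | Grade and frequency |

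Section 10.3.2 requires all AEs to be recorded whatever their severity, but it acts only after a finding has been called an AE. It does not settle the second step.

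**3. Grading passages side by side.** Section 10.1.3 restricts CTCAE 4.03 to nonhematologic AEs. Its fallback scale covers only events not listed in CTCAE, so it names no scale for hematologic events. Section 7.1.1 uses CTCAE 4.03 for AE information generally. Section 5.3.1.5 gives grade 4 neutrophils as below 500, grade 3 platelets as below 50,000 and grade 4 platelets as below 25,000 per microlitre. The monitoring form in Appendix 5 asks for grade 3, 4 and 5 AEs by CTCAE category. Hematologic grading is therefore contradictory, not absent.

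**4. Baseline.** The platelet entry limit (above 50,000) meets the grade 3 cut-off in Section 5.3.1.5 (below 50,000). A patient who enters just above the limit becomes grade 3 after a trivial fall. For neutrophils, a fall from 750 to 500 is 250/750, or one third, and anything below that is grade 4. A patient who starts from a normal count and reaches the same grade has had a much larger fall. AE frequency counts each as one event.

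**5. Size, by assumption only.** The documents give neither the true rate *p* of laboratory grade 3-4 cytopenia in these patients nor the share *f* of affected patients recorded as having an AE. Take N = 35, which is a maximum because 35 is the number to be consented (Section 9.5) and toxicity evaluation needs at least one dose. Assume that patients are independent.

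- Expected patients in the table = 35 × p × f
- Chance that no grade 3-4 cytopenia is tabulated = (1 − p × f)^35

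Each cell gives the expected number, then that chance:

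| p (expected true cases) | f = 100% | f = 75% | f = 50% | f = 25% |
|---|---|---|---|---|
| 10% (3.5) | 3.5; 2.5% | 2.6; 6.5% | 1.75; 16.6% | 0.9; 41.2% |
| 20% (7.0) | 7.0; 0.04% | 5.25; 0.3% | 3.5; 2.5% | 1.75; 16.6% |
| 30% (10.5) | 10.5; under 0.01% | 7.9; 0.01% | 5.25; 0.3% | 2.6; 6.5% |

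Example: with p = 10% and f = 25%, (1 − 0.025)^35 = 0.412. That is the least favourable corner. At f = 100% nothing is lost.

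**The case against.** A reader might infer that grade 3-4 cytopenia *would* be under-reported, that the rate is biased downward, or that hematologic events cannot be graded at all. The documents do not support any of these.

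- **The AE definition is broad.** Section 10.1.1 covers any untoward medical occurrence. The laboratory wording is an example, the list that follows is open-ended, and Section 10.3.1 also admits findings detected by other means. Section 10.1.1 does expressly exclude asymptomatic treatment-related lymphocytosis, but it has no such exclusion for low counts. This stands: clinical significance is discretionary wording, not a demonstrated filter.
- **A scale exists.** Sections 7.1.1 and 5.3.1.5 and Appendix 5 all give or assume hematologic grades. This stands. A conflict over scale does not by itself lower rates.
- **Dose rules do not define AEs.** Section 5.3.1.5 acts on grade 4 neutropenia "for more than 7 days. See Section 6 for instructions regarding the use of growth factor support". It is tempting to conclude that shorter episodes would be judged insignificant, but no section ties clinical significance to a dose change. The same section covers any grade 4 thrombocytopenia and has a general clause for other serious toxicity.
- **Cytopenias do get reported.** The pooled ibrutinib data in Section 1.5 list neutropenia first among reported grade 3-4 events, with thrombocytopenia and anemia also listed. The recording rules of those studies are not shown, so this is reassuring but not decisive.
- **Baseline is partly handled.** Section 10.1.1 does not count a pre-existing condition unless it worsens, so stable low counts should not be tabulated. That is right. It still does not show the size of a change. Nor can a shift table in a single arm separate drug effect from disease or earlier therapy.

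None of this supplies the missing analysis of the counts.

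**Conclusion.** The gap is real but modest. Section 9.4.2 leaves frequently collected blood counts out of the safety analysis although cytopenia is a named risk and safety a stated objective. Asymptomatic grade 3-4 cytopenia could be under-reported and sites could differ. The loss depends on recording practice, cannot be computed from the documents and may be zero. Every non-zero figure above rests on assumed values of p and f. The 41% is the chance of no tabulated grade 3-4 *cytopenia* at one extreme pair of assumptions, not the chance of a table with no grade 3-4 event of any kind.

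Two parts do not depend on those assumptions: AE frequency does not show change from baseline, and Sections 10.1.3 and 7.1.1 contradict each other on grading. The primary response analysis is unaffected. This is a worthwhile, inexpensive improvement to the safety reporting.

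**What to change.** **Section 9.4.2.** For all patients who receive at least one dose, add the worst post-baseline CTCAE v4.03 grade computed from the recorded neutrophil, platelet and hemoglobin values, whether or not the value was reported as an AE. Present it as a shift table from the Cycle 1 Day 1 value, with the number and percentage newly reaching grade 3 and newly reaching grade 4. A patient already at grade 3 at baseline counts only on reaching grade 4. Keep the AE table beside it, so that any difference between the two is visible.

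**Section 10.1.3.** Reconcile it with Section 7.1.1 so that one stated scale grades hematologic AEs.

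**Optional.** Do the same for AST, ALT, bilirubin and creatinine, which are also collected.

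**Cost.** No new tests or visits. There is some extra table work. Section 12.5 names the electronic data capture system but does not say that numeric laboratory results are entered, so data entry may be needed. The optional chemistry table may also need local reference ranges. The reported grade 3-4 rates may look less favourable.

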#### **9.4.3. Biomarker Analyses**

- Pre/Post Th1 Th2 Changes for ORR+ and ORR- individuals

McNemar's test will be used to evaluate the statistical significance of pre /post therapy changes in Th1 and Th2 positivity separately for those who have an ORR and for those who do not. A conditional logistic regression model will be used to explore whether pre-post changes in Th1 and Th2 are predictive of ORR.

- Association of PDL1 and PDL2 positivity with ORR

The association between PDL1 and PDL2 positivity will be explored using Fisher's exact test. A logistic regression model will be used to explore the association of PDL1 and PDL2 copy gain with ORR.

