	
 
• Requires treatment with a strong cytochrome P450 (CYP) 3A4/5 inhibitor. (see Appendix 3)
 
• Currently active, clinically significant hepatic impairment Child-Pugh class B or C according to the Child Pugh classification
 
• Lactating or pregnant.
 
• Unwilling or unable to participate in all required study evaluations and procedures.
 
• Unable to understand the purpose and risks of the study and to provide a signed and dated informed consent form (ICF) and authorization to use protected health information (in accordance with national and local subject privacy regulations).
 

Study Treatment:	Ibrutinib 560mg p.o. q.d. until disease progression, unacceptable toxicity or patient/clinician choice to discontinue.
Concomitant Therapy:	Refer to Section 6 for information on concomitant therapy.
Safety Plan:	The Barbara Ann Karmanos Cancer Institute, Data and Safety Monitoring Committee (DSMC), provides the primary oversight of data and safety monitoring for KCI Investigator-initiated trials. In Addition monthly investigator teleconferences will occur to discuss adverse event and safety issues.
Statistical Methods and Data Analysis:	
All efficacy analyses will be performed using all evaluable participants.
 
Primary Efficacy Analysis:  A one-sample binomial test will be used to assess efficacy in terms of ORR. The ORR will be reported as a proportion with a one-sided, lower 95% confidence interval. Assuming p0=30%, pA=50%, power=85% and type I error = 10.69% the null hypothesis will be rejected if there are 13 or more ORRs.
 
Secondary Efficacy Analysis:  DOR will be reported as median and range. Kaplan-Meier estimate of median PFS will be reported with 95% confidence intervals.
 
Exploratory Efficacy Analysis:

	
The influence of ibrutinib on T cell behavior and antitumor effect will be assessed using a variety of techniques including gene expression and mutational analysis. T cell subset alterations in blood and tumor tissue will be analyzed and PD-1 and PD-2 expression will be evaluated by FISH and IHC.
 
Safety Analysis:
 
Frequency of grade 3 or higher adverse events will be tabulated and all grade 1 and 2 adverse events will be collected.

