### 7.1.2. Pharmacokinetics/Biomarkers

- To assess ibrutinib's influence on T cell behavior and antitumor effect, serial serum samples pre and post therapy will be assessed for Th1 ( (IFN- $\gamma$  ) and Th2 cytokines ( IL-10, IL-4 and IL-13) at 4 distinct time points (pre-dose cycle 1 day one, pre-dose cycle 1 day 2 , pre-dose cycle 1 day 15) , and pre-dose cycle 2 day 1 (See **Appendix 1**). All assessments will occur prior to dosing that day.

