#### **9.3.3. Exploratory Endpoints**

The influence of ibrutinib on T cell behavior and antitumor effect will be assessed using pre-therapy and post therapy flow cytometry measures of Th1 and Th2 at predetermined time points in therapy.

PDL1 and PDL2 copy number analysis on paraffin-embedded tissue sections will be assessed by FISH.

All patients undergoing any exploratory evaluations will be assessed for correlative analysis.

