### **9.5. Sample Size Determination**

A study of 31 evaluable participants was deemed feasible. To accomplish this with an expected dropout not evaluable rate of 12%, a total sample population of 35 patients will be consented. We specified statistical power of 85% to distinguish a null hypothesis value of 30% against an alternative value of 50% assuming a binomial test of one proportion with a target, one-sided type error of 11%. Under these assumptions the null hypothesis will be rejected if there are 13 or more ORRs among the 31 participants.

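### The Th1/Th2 biomarker tests in Section 9.4.3 use one binary pair per patient and do not compare responders with non-responders, and the model meant to link change to response cannot be estimated with patients as strata

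*Combined protocol and SAP*

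**What the plan says.** Section 9.4.3 states that "McNemar's test will be used to evaluate the statistical significance of pre /post therapy changes in Th1 and Th2 positivity", separately for patients with and without a response. Its next sentence plans a conditional logistic regression to explore whether pre/post changes in Th1 and Th2 predict ORR.

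The measurements are richer than one pair. Section 7.1.2 says "serial serum samples pre and post therapy will be assessed for Th1" (IFN-gamma) and for Th2 (IL-10, IL-4 and IL-13), pre-dose at cycle 1 days 1, 2 and 15 and at cycle 2 day 1. Appendix 1 repeats these draws, adds one at progression, and labels them serum samples. Section 9.3.3 describes the endpoint differently, as "flow cytometry measures of Th1 and Th2 at predetermined time points in therapy".

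No section gives a cut-off for positivity, a rule combining three Th2 cytokines into one status, the visit that counts as post-therapy, the version of McNemar's test, or an alpha or power for the biomarker analyses. Section 9.1 makes this an exploratory objective, worded as estimation of the T cell subset alteration. Section 2.3 asks how biomarkers correlate with clinical outcomes.

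**The concern.** McNemar's test sees only patients who change category. A patient whose cytokine doubles without crossing the cut-off adds nothing, and neither do the draws outside the chosen pair. The result is a p-value within each group, whereas the stated objectives are to estimate the alteration and relate it to outcome.

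Running the test in each group also invites a familiar misreading. If it is significant in responders only, that can be taken as evidence that change predicts response, although no comparison was made. The regression would have to supply that comparison, so it matters whether it can be fitted.

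At stake is the information from four timed draws per patient, each taken with that day's dose withheld until afterwards.

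**Working it through.** **1. The plan's own figures.** Section 9.5: "A study of 31 evaluable participants was deemed feasible", and "the null hypothesis will be rejected if there are 13 or more ORRs among the 31 participants". The exact binomial gives P(X ≥ 13 | n = 31, p = 0.30) = 0.1069, matching the synopsis (10.69%), and P(X ≥ 13 | n = 31, p = 0.50) = 0.8595, consistent with the stated 85%. There is no biomarker power figure to reproduce. Thirteen is the rejection boundary and not an expected count: 31 × 0.30 = 9.3 and 31 × 0.50 = 15.5. I therefore show 9, 13 and 16 responders.

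**2. What exact McNemar needs.** With m discordant patients all moving one way, the two-sided p is 2 × 0.5^m. For m = 5 it is 0.0625; for m = 6 it is 0.031. At least six one-directional changers are needed for p ≤ 0.05.

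**3. How many changers to expect (one case).** Take pre ~ N(0,1) and post ~ N(1,1), correlation 0.5, positive if above the baseline median. P(both negative) = 0.1274. Negative-to-positive is 0.5 − 0.1274 = 0.3726. Positive-to-negative is 0.1587 − 0.1274 = 0.0313. Discordance is 0.4039, so 13 responders yield 13 × 0.4039 = 5.25 changers on average. That is fewer than six, even for a shift of a full SD.

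**4. Within-group power.** Assumptions, none from the documents: paired normal values, fixed cut at the baseline median, two-sided 0.05, shifts in baseline SDs. Simulated power in %, correlation 0.5 / 0.7:

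| Responders | Test | 0.5 SD | 0.8 SD | 1.0 SD |
|---|---|---|---|---|
| 9 | exact McNemar | 1 / 1 | 4 / 3 | 6 / 5 |
| 13 | exact McNemar | 6 / 5 | 16 / 16 | 26 / 26 |
| 16 | exact McNemar | 10 / 10 | 28 / 30 | 42 / 46 |
| 13 | mid-p McNemar | 13 / 12 | 30 / 31 | 44 / 46 |
| 13 | uncorrected McNemar | 21 / 22 | 41 / 48 | 57 / 64 |
| 13 | signed-rank | 35 / 55 | 72 / 92 | 90 / 99 |
| 13 | paired t | 38 / 58 | 75 / 93 | 91 / 99 |

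For group sizes of 9, 13, 16 and 18, correlations of 0, 0.5 and 0.7, and these shifts, the paired t test beat every version of McNemar. So did the signed-rank test, apart from one tie with the uncorrected version (9 patients, correlation 0, shift 0.5 SD).

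**5. The conditional logistic model.** A stratum's likelihood is the probability of its observed outcomes divided by the sum over all rearrangements of those outcomes within the stratum. If the stratum is a patient and the outcome is ORR, every row has the same value. There is only one arrangement, so the contribution is 1 whatever the coefficient. Fitted to a simulated data set, the model dropped all 31 strata.

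**6. Between-group power of a continuous analysis.** Compare mean change in 13 v 18 patients, with difference d in SDs of change. The noncentrality is d × √(13 × 18 / 31) = 2.747d, with 29 df and critical t = 2.045. Power is 26%, 57% and 76% for d = 0.5, 0.8 and 1.0.

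**The case against.** The strongest objection is that the plan does link change to response. A reader of the McNemar sentence alone might infer that the groups are never compared. The documents do not support that, because the following sentence plans a regression for this purpose. What stands is narrower: the McNemar tests do not compare the groups, and the regression fails on its natural reading. Other readings exist. The term might mean exact logistic regression with one record per patient, which can be estimated. The model might instead take time as outcome, with a Th-by-ORR term. That can be fitted in principle, but in one simulated data set of this size the coefficient was 13.4 with a standard error of 528. The text names neither reading and no other strata.

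A reader might also infer that the serial values are discarded altogether. That goes too far. Positivity appears only in the McNemar sentence, and Section 1.7 says the pre- and post-therapy cytokine profiles will be compared, without naming a method.

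Nor are the power figures properties of this trial. They move with the responder count, the cut-off, the correlation and the version of the test. With 18 patients and a 1.0 SD shift, exact McNemar reaches 54% to 58%, so it would be wrong to say that real shifts will usually be missed in every group.

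Finally, the flow cytometry wording does not prove a mismatch with what is collected. Section 7.4 mentions blood samples for T cell behaviour and cytokine expression and defers details to a Lab Manual that is not among the documents. If positivity is a flow cytometry result, the McNemar test is not a dichotomy of the serum values. The passages need reconciling, no more.

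**Conclusion.** The point holds as an efficiency and specification weakness in an exploratory analysis. Three parts do not rest on assumed effect sizes: each McNemar test uses one binary pair per patient, separate within-group tests do not compare the groups, and a patient-stratified conditional logistic model with ORR as outcome carries no information.

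The size of the power loss is conditional on the assumptions in step 4. Exact McNemar has about 1% to 6%, 5% to 26% and 10% to 46% power with 9, 13 and 16 responders. With 13, uncorrected McNemar has about 21% to 64% and the signed-rank test about 35% to 99%. The direction is stable; the figures are a scenario.

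It is tempting to read the signed-rank figures as what a better plan would achieve for the responder comparison. They are within-group figures and do not carry over: that comparison has about 26% to 76% power. The plan promises no biomarker power, and the ORR decision is untouched. The change is worth making because it is cheap, but it is not critical.

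**What to change.** Revise Section 9.4.3:

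- Analyse log cytokine concentration as a continuous variable over all four pre-dose draws in a mixed model with time, ORR status, time-by-ORR and a random patient intercept. Report estimates with confidence intervals. This is one reasonable choice among several.
- Use a signed-rank or paired t test as the simple within-group summary, with the post-therapy visit named in advance. If positivity is kept as a description, define the cut-off and how the three Th2 cytokines combine.
- Replace the conditional logistic model with the time-by-ORR term, or with ordinary or exact logistic regression of ORR on each patient's change.
- State that between-group power is limited (about 26%, 57% and 76% for differences of 0.5, 0.8 and 1.0 SD of change, 13 v 18), so the results are for estimation.
- Reconcile the flow cytometry wording in Section 9.3.3 with the serum samples in Section 7.1.2 and Appendix 1.

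The cost is SAP wording and slightly more analysis work. No new samples are needed.
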